**Less common known potential toxicities, 1% - 10%:**

**Cardiovascular:** Atrial fibrillation, atrial flutter

**Renal:** Increased serum creatinine

**Limited to important or life threatening:** Abnormal platelet aggregation, hepatic failure, hypersensitivity (includes anaphylactic shock, angioedema, urticaria), interstitial pulmonary disease, onychoclasia, pneumonia due to *Pneumocystis carinii*, pneumonitis, progressive multifocal leukoencephalopathy, renal failure, Stevens-Johnson syndrome, tumor lysis syndrome

15.28 **Drug procurement:** Commercial supplies. Pharmacies or clinics shall obtain supplies from normal commercial supply chain or wholesaler.

15.29 **Nursing Guidelines:**

- There are numerous drug to drug interactions. Record all of patient's medications including OTC, and herbal use. Avoid concomitant use with agents as listed in section 15.16.
- Ibrutinib should be taken with water at approximately the same time each day and can be taken with or without food. Capsules should be swallowed whole.
- Patients should be instructed to avoid eating grapefruit (including juice) and Seville oranges while on ibrutinib.
- Peripheral edema is common. Instruct patients to report this to the study team.
- Gastrointestinal side effects are common (diarrhea, nausea, constipation, abdominal pain, vomiting, etc). Treat symptomatically and monitor for effectiveness of intervention.
- Monitor CBC w/diff. Instruct patients in energy conserving lifestyle (anemia) and to report any unusual bruising or bleeding and/or signs or symptoms of infection to study team.
- Arthralgias, myalgias, and muscle spasm can be seen. Treat symptomatically and monitor for effectiveness.
- Monitor renal function/uric acid levels, especially in patients who may be experiencing dehydration.
- Respiratory symptoms may include, cough, SOB, and URI. Instruct patients to report these symptoms to the study team.
- Rarely patients can experience secondary skin cancers. Instruct patients to report any new skin lesions to the study team.
- Rash can be seen. Instruct patient to report to study team.
- Cardiac arrhythmias have been seen with this agent including a-fib, atrial flutter and ventricular tachyarrhythmia's, some of which have led to death. Instruct patients who experience any palpitations, lightheadedness, syncope, or SOB to see medical care immediately. This is especially important in patients who have pre-existing cardiac issues.

## 16.0 Statistical Considerations and Methodology

### 16.1 Overview

This is a Phase II, single arm, open-label, study to assess the safety, tolerability, pharmacokinetics and pharmacodynamics of the combination of ibrutinib and ixazomib administered to patients with WM.

16.11 Primary Endpoint: The primary endpoint of this trial is the rate of complete response. A complete response is defined as an objective status of CR per Appendix III at any time, where confirmation of the complete response status is required on two consecutive evaluations with a second immunofixation before calling the patient a CR. All patients meeting the eligibility criteria, who have signed a consent form and have begun treatment, will be evaluable for response, unless they are determined to be a major violation.

### 16.2 Statistical Design

16.21 Decision Rule: The largest success proportion where the proposed treatment regimen would be considered ineffective in this population is 5%, and the smallest success proportion that would warrant subsequent studies with the proposed regimen in this patient population is 20%. The following one-stage design with an interim analysis is based on a two-stage Simon optimum design and requires 37 evaluable patients to test the null hypothesis that the true success proportion in this patient population is at most 5%.

16.211 Interim Analysis: Enter 12 evaluable patients into the study. If no successes are observed in the first 12 evaluable patients, we will consider this regimen ineffective in this patient population and terminate the study. Otherwise, if the number of successes is at least 1, we will continue accrual.

16.212 Final Decision Rule: Enter an additional 25 evaluable patients into the study. If 3 or fewer successes are observed in the first 37 evaluable patients, we will consider this regimen ineffective in this patient population and terminate this study. Otherwise, if the number of successes is at least 4, this will be considered evidence of promising activity and the treatment may be recommended for further testing in subsequent studies in this population.

16.213 Over Accrual: If more than the target number of patients are accrued, the additional patients will not be used to evaluate the stopping rule or used in any decision making process. Analyses involving over accrued patients are discussed in Section 16.313.

16.214 NOTE: We will not suspend accrual at the interim analysis to allow the first 12 patients to become evaluable, unless undue toxicity is observed. Given the limited overall sample size and the inclusion of an AE stopping rule, we feel it is ethical to not halt accrual for the interim analysis. However, if accrual is extremely rapid, we may temporarily suspend accrual in order to obtain safety data on these patients before re-opening accrual to further patients.

16.215 Dose de-escalation in safety analysis: A safety analysis will be performed in the first 6 evaluable patients per Section 16.4. In the case of unacceptable toxicity, the dose of ixazomib will be de-escalated (Table 7.1b). If this occurs, the first 6 patients will be evaluated separately and will not be included in any decision making criteria.

16.22 Sample Size: The one stage study design with an interim analysis to be utilized is fully described above. A minimum of 12 and a maximum of 37 evaluable patients will be accrued onto this phase II study unless undue toxicity is encountered. If dose de-escalation is required during the safety analysis, an additional 6 evaluable patients will be accrued per Section 16.4. We anticipate accruing an additional up to 4 patients to account for ineligibility, cancellation, major treatment violation, or other reasons for a total of up to 47 patients.

16.23 Accrual Rate and Study Duration: The anticipated accrual rate is 2 evaluable patients per month. At this rate, it will likely take about 2 years to enroll all patients. The maximum study duration is expected to be approximately 7 years, or until the last patient accrued has been followed by 5 years.

16.24 Power and Significance Level: Power and Significance Level: Assuming that the number of successes is binomially distributed, the significance level is .09, i.e. there is a 9% chance of finding the drug to be effective when it truly is not. The probability of declaring that this regimen warrants further study (i.e. statistical power) and the probability of stopping at the interim analysis under various success proportions can be tabulated as a function of the true success proportion as shown in the following table.

If the true success proportion is...	0.05	0.10	0.15	0.20
Then the probability of declaring that the regimen warrants further study is...	0.09	0.45	0.75	0.90
And the probability of stopping at the interim analysis is...	0.54	0.28	0.14	0.07

16.25 Other Considerations: AEs, quality/duration of response, and patterns of treatment failure observed in this study, as well as scientific discoveries or changes in standard care will be taken into account in any decision to terminate the study

### 16.3 Analysis Plan

The analysis for this trial will commence at planned time points (see 16.2) and at the time the patients have become evaluable for the primary endpoint. The Statistician and Study Chair will make the decision, in accord with CCS Standard Operating Procedures, availability of data for secondary endpoints (e.g., laboratory correlates), and the level of data maturity. It is anticipated that the earliest date in which the results will be made available via manuscript, abstract, or presentation format is when last patient has been followed for at least 6 months.

**16.31 Primary Outcome Analysis**

16.311 Definition: The primary endpoint of this trial is the complete response rate. A success is defined as an objective status of CR per Appendix III at any time, where confirmation of the complete response status is required on two consecutive evaluations with a second immunofixation before calling the patient a CR. All patients meeting the eligibility criteria who have signed a consent form and have begun treatment will be evaluable for response, unless they are determined to be a major violation.

16.312 Estimation: The proportion of successes will be estimated by the number of successes divided by the total number of evaluable patients. 95% confidence intervals for the true success proportion will be calculated according to the approach of Duffy and Santner.

16.313 Over Accrual: If more than the target number of patients are accrued, the additional patients will not be used to evaluate the stopping rule or used in any decision making processes; however, they will be included in final point estimates and confidence intervals.

**16.32 Secondary Outcome Analysis**

16.321 The overall response rate will be estimated by the total number of patients who achieve a CR VGPR, or PR divided by the total number of evaluable patients. All evaluable patients will be used for this analysis. Exact binomial 95% confidence intervals for the true overall response rate will be calculated.

16.322 Time to progression is defined as the time from registration to the earliest date of documentation of disease progression. The distribution of time to progression will be estimated using the method of Kaplan-Meier.

16.323 Overall survival is defined as the time from registration to death due to any cause. The distribution of overall survival will be estimated using the method of Kaplan-Meier.

16.324 AEs: All eligible patients that have initiated treatment will be considered evaluable for assessing AE rate(s). The maximum grade for each type of AE will be recorded for each patient, and frequency tables will be reviewed to determine patterns. Additionally, the relationship of the AE(s) to the study treatment will be taken into consideration.

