#### 10.4 Expedited Reporting Requirements for IND Agents

##### 10.4.1 Phase 1 and Early Phase 2 Studies: Expedited Reporting Requirements for Adverse Events that Occur on Studies under an IND within 30 Days of the Last Administration of the Investigational Agent/Intervention 

**FDA REPORTING REQUIREMENTS FOR SERIOUS ADVERSE EVENTS (21 CFR Part 312)**

**NOTE:** Investigators **MUST** immediately report to the sponsor **ANY** Serious Adverse Events, whether or not they are considered related to the investigational agent(s)/intervention (21 CFR 312.64)

An adverse event is considered serious if it results in **ANY** of the following outcomes:

- 1) Death
- 2) A life-threatening adverse event
- 3) An adverse event that results in inpatient hospitalization or prolongation of existing hospitalization for  $\geq 24$  hours
- 4) A persistent or significant incapacity or substantial disruption of the ability to conduct normal life functions
- 5) A congenital anomaly/birth defect.
- 6) Important Medical Events (IME) that may not result in death, be life threatening, or require hospitalization may be considered serious when, based upon medical judgment, they may jeopardize the patient or subject and may require medical or surgical intervention to prevent one of the outcomes listed in this definition. (FDA, 21 CFR 312.32; ICH E2A and ICH E6).

**ALL SERIOUS** adverse events that meet the above criteria **MUST** be immediately reported to the sponsor within the timeframes detailed in the table below.

Hospitalization	Grade 1 and Grade 2 Timeframes	Grade 3-5 Timeframes
Resulting in Hospitalization $\geq 24$ hrs	7 Calendar Days	24-Hour 3 Calendar Days
Not resulting in Hospitalization $\geq 24$ hrs	Not required	

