## 10.52 Death

**Note: A death on study requires both routine and expedited reporting regardless of causality, unless as noted below. Attribution to treatment or other cause must be provided.**

Any death occurring within 30 days of the last dose, regardless of attribution to an agent/intervention under an IND requires expedited reporting within 24-hours.

Any death occurring greater than 30 days with an attribution of possible, probable, or definite to an agent/intervention under an IND requires expedited reporting within 24-hours.

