## 10.6 Required Routine Reporting

### 10.61 Baseline and Adverse Events Evaluations

Pretreatment symptoms/conditions to be graded at baseline and AEs to be graded at each evaluation.

Grading is per CTCAE v4.0 **unless** alternate grading is indicated in the table below:

System Organ Class	Adverse event/Symptoms	Baseline	Each evaluation
Blood and lymphatic system disorders	Anemia	X	X
Gastrointestinal disorders	# of stools	X	
	Diarrhea		X
	Nausea		X
	Vomiting		X
General disorders and administration site conditions	Fatigue	X	X
Investigations	Neutrophil count decreased	X	X
	Platelet count decreased	X	X
Nervous system disorders	Peripheral motor neuropathy	X	X
	Peripheral sensory neuropathy	X	X

10.62 Submit via appropriate MCCC Case Report Forms (i.e., paper or electronic, as applicable) the following AEs experienced by a patient:

- Grade 2 AEs deemed *possibly, probably, or definitely* related to the study treatment or procedure.
- Grade 3 and 4 AEs regardless of attribution to the study treatment or procedure.
- Grade 5 AEs (Deaths)
- Any death within 30 days of the patient’s last study treatment or procedure regardless of attribution to the study treatment or procedure.
- Any death more than 30 days after the patient’s last study treatment or procedure that is felt to be at least possibly treatment related must also be submitted as a Grade 5 AE, with a CTCAE type and attribution assigned.

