### 13.5 Ineligibles

A patient is deemed *ineligible* if after registration, it is determined that at the time of registration, the patient did not satisfy each and every eligibility criteria for study entry. The patient may continue treatment off-protocol at the discretion of the physician as long as there are no safety concerns, and the patient was properly registered. The patient will go directly to the event-monitoring phase of the study (or off study, if applicable).

- If the patient received treatment, all data up until the point of confirmation of

ineligibility must be submitted. Survival follow-up will be required per the protocol.

- If the patient never received treatment, on-study material and the End of Active Treatment/Cancel Notification Form must be submitted. No further data submission is necessary.

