#### **16.4 Early Safety Analysis**

7.1 An early safety analysis will be performed after the first 6 evaluable patients have been accrued to the study and observed for one cycle. Accrual will be temporarily halted while these patients are evaluated. If 2 or more of the first 6 patients experience a significant toxicity as defined below, then the dose of ixazomib may be de-escalated (as per Table b). In this case, another safety analysis will be conducted on the first 6 evaluable patients treated at the reduced dose level.

Toxicity will be measured per NCI-CTCAE version 4. Significant toxicity is defined as an adverse event occurring during the first cycle of treatment that is possibly, probably, or definitely related to study treatment and that meets one of the following:

- Grade 3 diarrhea, nausea, and fatigue lasting > 3 days despite optimal supportive medications
- Any other  $\geq$  Grade 3 non-hematological toxicity with the exceptions of electrolyte abnormalities that are reversible and asymptomatic.
- Febrile neutropenia
- Grade 3 thrombocytopenia with clinically significant bleeding
- Any  $\geq$ Grade 4 neutrophil count decreased or platelet count decreased that persists >7 days

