#### **16.52 Adverse Event Stopping Rules**

The stopping rules specified below are based on the knowledge available at study development. We note that the AE Stopping Rule may be adjusted in the event of

either (1) the study re-opening to accrual or (2) at any time during the conduct of the trial and in consideration of newly acquired information regarding the AE profile of the treatment(s) under investigation. The study team may choose to suspend accrual because of unexpected AE profiles that have not crossed the specified rule below.

Accrual will be temporarily suspended to this study if at any time we observe events considered at least possibly related to study treatment (i.e. an AE with attribute specified as “possible,” “probable,” or “definite”) that satisfy one of the following:

- if 4 or more patients in the first 12 treated patients experience a grade 4 or higher non-hematologic AE at least possibly related to treatment.
- if after the first 12 patients have been treated, 30% of all patients experience a grade 4 or higher non-hematologic AE at least possibly related to treatment.

We note that we will review grade 4 and 5 AEs deemed “unrelated” or “unlikely to be related”, to verify their attribution and to monitor the emergence of a previously unrecognized treatment-related AE.

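### Section 16.324 restricts the AE rates to eligible treated patients, so a patient who took study drug and was later found ineligible drops out of them

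*Combined protocol and SAP*

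**What the plan says.** Section 16.324 sets the population for the AE analysis: "All eligible patients that have initiated treatment will be considered evaluable for assessing AE rate(s". Its next sentence says that the maximum grade of each type of AE is recorded per patient and that frequency tables are reviewed. It neither repeats the eligibility condition nor names another population.

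Section 13.5 defines an ineligible patient as one found, after registration, not to have met every entry criterion. It sets no time limit for that finding and provides for patients who have already been dosed: "If the patient received treatment, all data up until the point of confirmation of" ineligibility must be submitted. It adds "The patient will go directly to the event-monitoring phase of the study" and allows treatment to continue off protocol at the physician's discretion.

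Other safety provisions use other wording:

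- The stopping rule in 16.52 applies "if 4 or more patients in the first 12 treated patients experience a grade 4 or higher non-hematologic AE", and after that to all patients.
- The early safety analysis in 16.4 is "performed after the first 6 evaluable patients have been accrued to the study and observed for one cycle".
- Routine reporting in 10.62 covers "Grade 3 and 4 AEs regardless of attribution to the study treatment or procedure".
- Section 10.52 states: "Any death occurring within 30 days of the last dose, regardless of attribution to an agent/intervention under an IND requires expedited reporting".
- Section 16.51 gives the DSMB a review of accrual and safety data at least twice a year.

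None of 16.52, 10.62, 10.52 and 16.51 mentions eligibility.

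**The concern.** Characterising safety and toxicity is secondary goal 2.23, and 16.324 is its planned analysis. Exposure is what puts a patient at risk of an adverse reaction, so the usual set for AE rates is everyone who took study drug. Adding eligibility removes exposed patients because of a finding made after registration, possibly after the AE is already known. That finding would then change both the numerator and the denominator.

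The removed patients need not resemble the rest. Several entry criteria concern safety: the blood count, liver and renal limits in 3.15, and the cardiovascular, neuropathy and liver exclusions in 3.2. A patient who breached one of these might be more prone to toxicity, but the documents do not establish that.

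The plan is also uneven. A grade 4 non-hematologic event in such a patient could count towards suspending accrual under 16.52 and still be absent from the reported AE rate.

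**Working it through.** **1. Who is left out.** Three sections define the sets:

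- 16.324: eligible and treatment started.
- 16.311 (response): eligible, consented, treatment started, and not a major violation.
- 13.7: a cancel never receives study treatment.

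Major violations therefore stay in the AE rates and cancels were never exposed. The only exposed patients left out are those treated and then found ineligible under 13.5. No other section returns them; 16.313 deals only with over-accrual.

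**2. The plan's own figure.** Section 16.22 gives 37 evaluable patients, 6 more if the dose is de-escalated, and up to 4 more for losses: 37 + 6 + 4 = 47, as stated. Without de-escalation, 37 + 4 = 41. The whole allowance is 4/41 = 9.8% or 4/47 = 8.5% of patients. It covers ineligibility, cancellation, major violation and other reasons together, so it is not an estimate of treated ineligible patients. The documents give no such estimate.

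**3. One treated ineligible patient, common event.** Assume 41 treated, 40 of them eligible, with 8 events among the 40. Exact (Clopper-Pearson) 95% intervals:

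| Set | Rate | 95% CI |
|---|---|---|
| 16.324 as written | 8/40 = 20.0% | 9.05 to 35.65% |
| All treated, extra patient without the event | 8/41 = 19.5% | 8.82 to 34.87% |
| All treated, extra patient with the event | 9/41 = 22.0% | 10.56 to 37.61% |

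The rate can move either way, and the shift is far smaller than the width of the interval.

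**4. One treated ineligible patient, rare event.** If the event occurs only in that patient, 16.324 gives 0/40 (0 to 8.81%) where all treated patients would give 1/41 = 2.44% (0.06 to 12.86%).

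**5. How likely step 4 is.** Let p be the true event rate, the same for all patients and independent between them, with 40 eligible patients and k treated ineligible patients. The chance that the event is seen only among the k patients is (1 − p)^40 × [1 − (1 − p)^k].

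| p | k = 1 | k = 4 (extreme) |
|---|---|---|
| 1% | 0.669 × 0.0100 = 0.67% | 0.669 × 0.0394 = 2.64% |
| 2% | 0.446 × 0.0200 = 0.89% | 0.446 × 0.0776 = 3.46% |
| 5% | 0.129 × 0.0500 = 0.64% | 0.129 × 0.1855 = 2.38% |

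The k = 4 column is an extreme, because it gives every spare place to a treated ineligible patient. It also implies 44 treated patients, which is neither 41 nor 47. With 4 of 41 or 4 of 47 excluded, leaving 37 or 43 eligible, the p = 2% entry becomes 0.98^37 × 0.0776 = 3.7% or 0.98^43 × 0.0776 = 3.3%, so the choice hardly matters.

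The 8 events, the 40 eligible patients, p and k are all assumptions for illustration.

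**The case against.** The best case for leaving the text alone is that nothing of consequence depends on it. Eligibility is verified before a registration is accepted (6.2), so there may be no such patient. One patient moves a rate by far less than its sampling error. The summary is descriptive and has no test or threshold. Safety decisions rest on 16.52, which counts treated patients and also reviews grade 4 and 5 events called unrelated, and on the DSMB review in 16.51. All of this stands. It limits the importance of the point, but it gives no reason to leave exposed patients out of the planned analysis of a secondary goal.

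It is also fair that the frequency-table sentence does not say eligible. Exclusion from the tables is the natural reading because the sentence follows directly, but it is not stated.

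A further objection bears on the remedy. Section 13.5 lets these patients continue off protocol. Counting every later SAE up to some interval after an unspecified last dose could bring off-protocol events into the trial's rates, and would collect serious and non-serious events over different periods. That is right, and the fix below is drawn accordingly.

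**Conclusion.** The point holds for the AE rates in 16.324: as written, treated patients later found ineligible are left out. For the frequency tables it is an inference. The effect is probably small and its direction is unknown. With one such patient and an assumed event rate of 1% to 5%, the chance that the summary misses an event entirely is below 1%. The change is worth making because it costs little and fixes the set before any AE is known.

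A reader might infer more than the documents support:

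- *That AEs in ineligible patients go unreported or escape oversight.* Sections 10.4.1, 10.52, 10.62, 16.51 and 16.52 carry no eligibility limit.
- *That the AE rates are biased downwards.* The rate falls only if the excluded patients had the event more often than the others; otherwise it is unchanged or rises.
- *That close to a tenth of patients would be lost.* The allowance of 4 also covers cancels, who are never treated, as well as major violations and other reasons.
- *That the early safety analysis in 16.4 has the same fault.* It uses the word evaluable, which is defined for response in 16.311 but not for that analysis. That is a separate question of definition.

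**What to change.** Replace the first sentence of 16.324 with:

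> AE rates and frequency tables will include all patients who received at least one dose of ixazomib or ibrutinib on protocol, regardless of eligibility, using the data submitted up to confirmation of ineligibility (Section 13.5) for patients found ineligible.

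Add a table footnote giving the number of such patients and noting their shortened observation. List separately, outside the rates, any SAE or death reported after confirmation of ineligibility. Keep the eligible set for response (16.311, 16.321) and leave 16.52 as worded.

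The cost is one revised sentence, a footnote and a short listing. No new data are needed: 13.5 already requires the data up to confirmation, and Section 10 already requires the later reports. Sample size, alpha and power rest on the response set and do not change. The downside is that AEs in these few patients may be under-recorded after confirmation of ineligibility, which the footnote discloses.
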